In an innovative use of an established and well validated intervention for insomnia, we propose to examine the direct effects of sleep on biomarkers of CVD risk outcomes among persons with PTSD and comorbid insomnia disorder (ID; see Figure 1). In this 2-arm RCT, 150 participants with PTSD and ID will be randomized at a 2:1 ratio to either CBT-I, or a minimal contact control condition (CCC). We anticipate that we may need to consent and screen as many as 500 participants to reach this goal. Sleep efficiency as measured by actigraphy will be the primary sleep outcome measure. Other parameters [total sleep time (TST) wake after sleep onset (WASO), sleep fragmentation] will be measured with a multi-modal assessment strategy including validated self-report measures, sleep diaries collected *via* Qualtrics, and objective sleep measurement (i.e., actigraphy). Sleep diaries and actigraphy will be continuously collected for 10-weeks (including a week-long baseline, 8-week period for CBT-I or CCC, and one-week post treatment) and for a week-long period at the 6-month follow-up. The primary outcomes for this clinical trial are established biomarkers of CVD risk, including flow mediated dilation, SNS activity, nighttime BP, nighttime BP dipping, and ASCVD risk. These biomarkers will be assessed at three time points: baseline, post-intervention (8-weeks), and 6-month follow-up. The 6-month follow-up period will allow us to evaluate whether the intervention effects on CVD risk are sustained beyond the immediate post-intervention period. Timing for the 6-month follow-up visit will be 6 months after

the baseline assessment or three months after the post-intervention assessment, whichever is later. Participants in both arms will continue with usual medical care.

C.2. Recruitment

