In the event of any equipment malfunction, participants may be asked to repeat the WatchPAT home study. In order to reliably rule out obstructive sleep apnea, a minimum of 4 hours of recording time is required. Therefore, if participants notice any of the equipment coming off in the middle of the night, they will be instructed to reattach. If it is found that there is less than 4 hours of recording time, the participant will be asked to repeat the in-home study. To prevent this from occurring, participants will be given detailed instructions and staff will provide an in-person demonstration to show them how to properly use the device.

C.5.2.3. Actigraphy. Actiwatch Spectrum Plus® (Respironics, Inc.) are wristwatch style actigraphs containing a calibrated accelerometer that samples, digitizes, and stores movement activity. When interfaced with a computer, a scoring algorithm provides estimates of various sleep parameters. When costly PSG is not feasible and sleep staging outcomes are not the focus of research, wrist actigraphy is recommended as an essential measure of rest-activity patterns in insomnia research (Buysse, Ancoli-Israel, Edinger, Lichstein, & Morin, 2006). The following sleep metrics will be collected over a one week period at baseline, post-treatment, and 6-month follow-up: Time in Bed (TIB), TST, WASO, and sleep fragmentation (Ancoli-Israel, Cole, Alessi, Chambers, Moorcroft, & Pollack, 2003; Blackwell et al., 2008; Littner et al., 2003; Marino et al., 2013; Morgenthaler et al., 2007; Sadeh & Acebo, 2002; Sadeh, Hauri, Kripke, & Lavie, 1995; Thorpy et al., 1995). These parameters will also be collected during the entire 8-

week treatment period.

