The study is designed as a two-arm trial to examine the effects of CBT-I on objective sleep parameters and CVD risk biomarkers. Statistical analyses will be performed using SAS, version 9.4 (SAS Institute, Cary, NC) and Mplus, version 7 (Muthén & Muthén, 2012). The first step in the analysis will be to calculate descriptive statistics, including graphical displays, to summarize all study variables. We will construct individual and mean trajectory plots of the longitudinal outcome variables to understand their general trends from baseline to post-intervention and 6-month follow-up. In addition, we will explore the variability and correlation structure of the longitudinal outcome variables. We will stratify by trauma exposure (combat or non-combat) and objectively measured sleep duration (<6 hours or \geq 6 hours).

Each of the study hypotheses will be examined using data collected at baseline, immediately following the 8-week intervention phase (i.e., post-intervention), and again at 6-month follow-up. Given nesting of these multiple observations within each participant, multilevel modeling (MLM) will be used to examine each set of hypotheses. MLM is a technique for analyzing repeated observations of data across multiple individuals (Searle, Casella, & McCulloch, 1992). Unlike repeated-measures ANOVA,

MLM uses all available data and can handle data missing at random. MLM can also accommodate imbalanced data and unequal variances.

To manage the problem of random positive findings when making multiple comparisons within each hypothesis (i.e., random significant findings occurring due to multiple proposed analyses), we will correct alpha using the “false discovery rate approach” described by Glickman (Glickman, Rao, & Schultz, 2014). This methodology differentiates random findings from hypothesis-driven outcomes and is more powerful than Bonferroni-type alpha adjustments that control the false-positive rate (Benjamini, 2010; Glickman, Rao, & Schultz, 2014; Schafer & Olsen, 1988; Searle, Casella, & McCulloch, 1992; Simes, 1986). Specifically, alpha correction will be applied to Aims 1 and 2 but not to the Supplemental Aim, given that any exploratory hypothesis that is supported would require validation with further research.

D.2. Missing Data Considerations

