MLM can accommodate data missing at random, using maximum likelihood-derived estimates based on all available data. That said, data may be missing not at random (MNAR). That is, the outcome data may be systematically missing, for instance, from participants who experience no benefit from CBT-I. Nevertheless, even in the case of MNAR data, estimates derived from analyses examining Hypothesis 2 (addressing the within-person associations of change in insomnia with change in CVD risk) and the Supplemental Aim are unlikely to be affected by data missingness. After all, even if participants who benefit the least from CBT-I drop out of the study, we still anticipate observing the same magnitude of association between improved sleep and changes in cardiovascular biomarkers and QoL. By contrast, Hypothesis 1, which examines clinical response to CBT-I, would be affected by MNAR data. As such, we will conduct sensitivity analysis on three missing data approaches for Aim 1. First, we will conduct a completer analysis, analyzing only data from participants who complete each of the three assessments. Second, we will allow the maximum-likelihood estimation to generate estimates for all available data. In a third approach, we will use an intent-to-treat approach, assuming that missing post-intervention and/or 6-month follow-up data are evidence of stagnation. Specifically, we will use last observation carried forward in the cases of missing data.

D.3. Primary and Secondary Analyses

To examine the degree to which CBT-I is associated with improved sleep efficiency and insomnia severity index score (manipulation check), linear MLM will be used to model sleep outcomes as a function of treatment (CBT-I, control), time (baseline, post-intervention, 6-month follow-up), and the interaction between treatment and time. Planned treatment contrasts in change from baseline to post-intervention and 6-month follow-up will be examined within the context of the model. To determine the degree to which CBT-I is associated with improved CVD risk biomarkers (Hypotheses 1a), each of the 6 CVD risk variables (24-hr SBP, nighttime SBP dipping, FMD, 24-hr epinephrine, and norepinephrine) will also be modeled as a function of treatment, time, and their interaction, with planned treatment contrasts in change from baseline at post-intervention and 6-month follow-up. Dichotomized 10-year ASCVD risk scores (Hypothesis 1b) and QoL scores (Hypothesis 1c) will similarly be modeled via logistic MLM.

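### If CBT-I non-responders drop out, the three-visit sleep models modestly overstate the sleep-efficiency effect, and the treatment-week data that would largely correct this are left out

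*Combined protocol and SAP*

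**What the plan says.** **Collection.** C.1 (Study Design Overview): "Sleep diaries and actigraphy will be continuously collected for 10-weeks". It breaks this down as one baseline week, the eight weeks of CBT-I or control, and one week after treatment, with a further week at 6 months. C.5.2.3 (Actigraphy) says of time in bed, total sleep time, wake after sleep onset and fragmentation: "These parameters will also be collected during the entire" eight-week treatment period. The same section defines sleep efficiency as total sleep time over time in bed, so a weekly value can be computed.

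**Role.** C.1: "Sleep efficiency as measured by actigraphy will be the primary sleep outcome measure". The Specific Aims and D.3 treat sleep efficiency and insomnia severity as the manipulation check. C.1 names the cardiovascular biomarkers as the primary outcomes.

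**Analysis.** D.1 says that each hypothesis will be "examined using data collected at baseline, immediately following the 8-week intervention phase (i.e., post-intervention), and again at 6-month follow-up". D.3 uses linear multilevel models to "model sleep outcomes as a function of treatment (CBT-I, control), time (baseline, post-intervention, 6-month follow-up), and the interaction between treatment and time". The Supplemental Aim sleep models use the same three visits, and D.4 counts at most two change scores per person for Hypothesis 2. No model uses a treatment week as outcome or auxiliary. At most those weeks fall under the descriptive summaries in D.1.

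**Missing data.** D.2 warns that "the outcome data may be systematically missing, for instance, from participants who experience no benefit from CBT-I" and accepts that Hypothesis 1 would then be affected. It plans three approaches: completers, maximum likelihood on all available data, and last observation carried forward (LOCF). It does not say whether the last observation may be a treatment week.

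**The concern.** Of 11 scheduled weeks of sleep recording (1 + 8 + 1 + 1), the models use three. Someone who leaves CBT-I after week 5 may have five weeks of measured response, but the three-visit likelihood sees only that person's baseline. It then in effect predicts the gain of a completer with the same baseline.

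Dropout that depends on observed treatment-week sleep is not missing at random to a model that omits those weeks. It becomes close to missing at random once they are included. The dropout D.2 fears is therefore partly a result of which data enter the likelihood.

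A difference between arms is plausible. C.4.2 offers controls CBT-I only after the 6-month visit, which gives them a reason to stay that a CBT-I non-responder lacks. At stake is the size of the CBT-I effect on the primary sleep measure.

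**Working it through.** **1. The plan's own figures count three observations per person.** Inputs from D.4: 150 participants, three time points, ICC 0.50, 10% loss at each of two steps.
- No loss: 450 / (1 + 2 × 0.5) = 225, as stated.
- With loss, 15 people give one visit, 13.5 give two and 121.5 give three: 15 + 13.5 × 2/1.5 + 121.5 × 3/2 = 15 + 18 + 182.25 = 215.25 (stated: 215).
- With 215 split 2:1, power at d = 0.41 is 80.9% (stated: 80%).

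The figures reproduce without any treatment-week data.

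**2. What drives the bias.** For a fraction q of the CBT-I arm missing the post visit:

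bias ≈ q × (gain the model predicts for the dropouts − their true gain).

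It is zero if the dropouts resemble completers with the same baseline. It cancels if the same selection acts in both arms.

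**3. Loss before the post visit.**
- Table 3: 142 of 150 reach the post assessment, so 8/150 = 5.3%.
- D.4: 10%.
- C.3: 0 to 20% in the group's earlier studies. Here 20% is an upper case.

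**4. Simulation.** From the plan: 100 v 50, ICC 0.50 and d = 0.54 (the sleep-efficiency benchmark in D.4). Assumed: person-level response SD 0.4 and autoregressive weekly residuals. CBT-I dropout depends on sleep change in weeks 3-5, at an odds ratio of 2 per SD, an odds ratio of 4 per SD, or as strict loss of the lowest responders. Excess in the baseline-to-post contrast:

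| Loss | OR 2 | OR 4 | Lowest responders | With treatment-week means added |
|---|---|---|---|---|
| 5.3% | about 3% | about 5% | 9-10% | not run |
| 10% | about 5% | 9-10% | about 16% | -1% to +3% |
| 20% | 8-10% | about 18% | about 26% | -2% to +1% |

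Ranges within a cell are repeat runs.

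**5. In SD units at 10% loss.** 0.05 × 0.54 = 0.027 and 0.16 × 0.54 = 0.086. With ICC 0.50 and unit variance, the variance of a change is 2 × (1 − 0.5) = 1, so the standard error is about √(1/90 + 1/45) = 0.183. The bias is 0.027/0.183 = 0.15 to 0.086/0.183 = 0.47 standard errors. By the formula in step 2, these need prediction gaps of 0.27 and 0.86 SD, so the last column of dropouts is an extreme case.

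**6. Second set of assumptions.** Response SD 0.3 to 0.5, linear weekly ramp, dropout after week 4, true effect 0.54:

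| Dropout | Three-visit ML, 10% / 20% loss | With weekly data |
|---|---|---|
| Random | 0.54 / 0.54 | 0.54 |
| Response-driven, both arms | 0.54 / 0.54 | 0.54 |
| Poor CBT-I responders, partly driven | 0.60 / 0.63-0.65 | 0.54 |
| Poor CBT-I responders, strict | 0.62-0.63 / 0.68-0.71 | 0.54 |
| Good CBT-I responders leave | 0.48-0.49 / 0.43-0.45 | 0.54 |

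The pattern is the same, with somewhat larger upper ends (0.71/0.54 = 1.31).

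**7. LOCF under the assumptions of step 6.** Carrying baseline gives about 0.49 at 10% and 0.43 at 20% when dropout is random, and 0.55-0.60 when poor responders leave. Carrying the last treatment week gives 0.49-0.51 at 10% and 0.45-0.49 at 20% across those cases. Neither is a dependable correction.

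**The case against.** **The effect is small and conditional.** This stands. At 10% loss the bias is under half a standard error, and it needs dropout that is both response-driven and different by arm. D.4 also cites d = 1.48 for sleep efficiency in an earlier PTSD trial. Against that effect the same absolute bias is 0.027/1.48 = 2% to 0.086/1.48 = 6%. C.7.8 holds payment until the post-treatment recordings and labs, which favours attendance, although people who withdraw from CBT-I are paid to date.

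**The near-zero residual is partly built in.** This also stands. The simulated dropout was driven by the variable then added to the model, and every dropout had it recorded. If half of the dropouts lack weeks 3-5, about 2%, 5% and 7% remain at 10% loss.

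**The plan does not ignore the threat.** D.2 names the mechanism and plans LOCF as a no-further-change analysis. Carrying baseline under the step 4 settings gives about -2%, +3% and +13% at 10% loss, so it often pulls the right way. Step 7 shows why it cannot be relied on. A reader might infer that LOCF discards the treatment weeks and carries baseline, but D.2 does not say which value is carried. That is an ambiguity to settle.

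**The reach is limited.** A reader might infer that the cardiovascular conclusions rest on this estimate. They do not. Hypothesis 1a compares each biomarker directly between randomised arms, and biomarkers have no treatment-week measurements. The Insomnia Severity Index, the other half of the manipulation check, gains nothing either: it is scheduled at visits, and C.4.2 gives it weekly only to controls.

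**Conclusion.** The point holds for the sleep models and should be acted on. The plan records sleep in both arms through treatment, fears dropout by CBT-I non-benefiters, and then fits models that cannot see the sleep of those who leave during treatment. In that situation three-visit maximum likelihood overstates the sleep-efficiency effect by about 3-10% at 5% loss, 5-16% at 10% and 8-26% at 20%, against a true d of 0.54. The second set of assumptions reaches somewhat higher.

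These sizes rest on assumed response spread, autocorrelation, dropout timing and strength of selection, so they are illustrative. The documents do not support saying that the effect will be overstated: the bias vanishes under random or arm-alike dropout and reverses if good responders leave. Nor do they support saying that the weekly data remove it entirely, since very early leavers and non-wearers supply little, and dropout driven by unmeasured factors remains. Participants lost only after the post visit still contribute their post value. The primary biomarker contrasts are untouched.

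**What to change.** In D.2 and D.3:
- Keep the estimand and the post-intervention and 6-month contrasts.
- For the sleep-efficiency and diary models, enter treatment-week means (for example weeks 3-5 and weeks 6-8), with arm-specific means, as auxiliary outcomes in the likelihood. Use actigraphy for sleep efficiency and the diary equivalents for the diary models.
- Report this as the maximum-likelihood analysis under missing at random, with the three-visit fit beside it.
- If LOCF is kept for sleep, state that it carries the last observed treatment week, and label it a sensitivity analysis only.
- Tabulate by arm how many dropouts have usable treatment-week data, so that the reader can judge how much correction was possible.

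**Cost.** SAP wording and some extra programming. The data are already scheduled, and D.1 already names Mplus. Sleep early in treatment may be atypical, which is why the weeks enter as auxiliaries and not as the outcome. The correction is only partial when people leave very early or lack wear data.

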Our study team will use social media to reach potentially eligible participants. We have developed a Facebook page for posting IRB-approved study flyers and information for this and other studies in the Traumatic Stress and Health Research Laboratory, <https://www.facebook.com/Duke-Traumatic-Stress-and-Health-Research-Lab-379366159145563/>. We plan to place pictures of our study flyers on the Facebook page, and use Facebook's post boost to draw attention to the post. The post itself will say "Enroll now!" or "Now enrolling!" We will also plan to use Facebook ads to target potential participants within a 50-mile radius of Duke. If any participant contacts the email associated with the Facebook page ([contact], he/she will be sent an automatic email response.

Any participant who contacts by telephone the study coordinator or other study staff regarding the study will be provided more information, and will be interviewed using an IRB-approved telephone screening. If a participant is deemed potentially eligible in the telephone screen, he/she will be scheduled to attend a formal screening visit. We will send, via Duke secured email, appointment reminders to any participant who wants to receive them. Prior to beginning study procedures, the study staff member obtaining consent will explain the study in detail, provide the participant with an IRB-approved written consent form explaining the procedures and risks, and answer any questions. The consent form will be signed via RedCap. Participants are given the chance to thoroughly read the consent prior to participation. Participants are given a copy of the signed informed consent form, and are given phone numbers to call if they have additional questions about the consent form or the research, if they have any problems during the study, or if they have questions about participating in research studies in general. With regards to determination of decision making capacity of potential participants, our laboratory has a standard procedure for determining understanding of the study procedures, risks, and benefits. We utilize this procedure if we have any reason to suspect that the participant may have difficulty in the consent process (e.g., traumatic brain injury impacting cognitive function, active psychotic symptoms). In this procedure, the study coordinator providing the informed consent information evaluates understanding of the procedures at several different time points during the process by asking questions like "Do you understand what we're asking you to do?" and "Do you have any questions about the risks of the study? Can you tell me what you understand the risks to be?" Prior to having a participant sign consent, the study coordinator, who has clinical experience in working with persons with psychotic disorders, may ask the potential participant to outline the study procedures, risks, and benefits so that he can make sure that the participant is aware of them. If the participant is unable to summarize these, he/she will not be allowed to sign the informed consent form, and may be referred for other treatment. No study procedures will begin until informed consent has been obtained.

C.3. Patient Eligibility and Randomization

Participants must meet each of the following inclusion criteria:

- Are between 40-59 years old;
- Has a current diagnosis of chronic PTSD (at least 3 months duration) based on the Clinician Administered PTSD Scale DSM-5 version (Weathers et al., 2013);
- Has a current diagnosis of ID as defined in the International Classification of Sleep Disorders

(ICSD-3; American Academy of Sleep Medicine, 2014)

Participants who meet any of the following criteria will be excluded from participation:

- Has a history of CVD events, including myocardial infarction, stroke, transient ischemic attack, or coronary revascularization;
- Has diagnosis of congestive heart failure or coronary artery disease based on results of diagnostic testing;
- Has a current alcohol use or substance use disorder (those who meet lifetime but not current alcohol or substance use disorder will be included);
- Is currently participating in an evidence-based trauma focused therapy for PTSD (i.e., Prolonged Exposure, Cognitive Processing Therapy, or Eye Movement Desensitization and Reprocessing);
- Has cognitive impairment as evidenced by less than 20 on the Montreal Cognitive Assessment scale (MOCA; Nasreddine et al., 2005);
- Meets criteria for a psychotic spectrum disorder or bipolar disorder;
- Has severely impaired hearing or speech;
- Is pregnant;
- Does not use benzodiazepines for sleep, and if prescribed benzodiazepines for some other use (e.g., anxiety, panic attacks), uses them fewer than four times in a one month period.;
- Is not stable (medications and dose stable for one month) on any other current psychoactive and/or cardiovascular medications or will not be stable on these medications during the course of the study;
- Works night shift;
- Is participating in another interventional study to address insomnia;
- Has prominent suicidal or homicidal ideation (as assessed through a clinical interview);
- Has nonclinically significant or sub-threshold insomnia as indicated by a score of <8 on the Insomnia Severity Index;
- Has seizures (based on clinical interview and self-report);
- Has a body mass index of 45 or greater;
- Has sleep apnea (based on the overnight assessment described below) or a positive sleep apnea screen;
- Has restless leg syndrome (based on the *Duke Structured Interview for Sleep Disorders* (DSISD); Edinger, Wyatt, & Olsen, 2009), and that sleep disorder is the primary cause of their sleep complaint (participants with restless legs syndrome who also have insomnia disorder can be included in the study);
- Has an organic cause of sleep disruption that cannot be addressed by cognitive-behavioral changes (e.g., hyperthyroidism), as determined by the DSISD;
- Has excessive daytime sleepiness, defined as a score >15 on the Epworth Sleepiness Scale (ESS) or as determined by the DSISD;
- Does not complete sleep diary assessments within 6 hours of rising on at least 5 of the 7 days of the initial assessment period; or
- Cancels or no-shows for two or more Time 1 assessment appointments

- Has uncontrolled hypertension (screening office BP > 160/100 mm Hg)

Participants who cannot complete study procedures may be withdrawn by the PIs. If any participant is excluded due to uncontrolled hypertension seeks treatment and their blood pressure becomes adequately controlled {e.g., with a stable antihypertensive medication regimen}, they will become eligible to participate if their clinic/office blood pressure is lower than 160/100 mm Hg and they have been stable on their antihypertensive medication(s) for one month.

Because the physiological changes of pregnancy may impact study outcome, we will exclude women who self-report pregnancy. Urine samples will be assayed by a trained staff member using a Quidel QuickVue pregnancy test. These pregnancy tests will be completed for women of childbearing potential. We have developed a short interview for female participants; this interview will help us determine which female participants must have a urine pregnancy test, and when the test should be done. Female participants of childbearing potential who are not pregnant must agree to use appropriate contraception during the course of the study, and to notify study staff if they become pregnant during the study.

Dropout rates across psychological and pharmacologic studies in our clinic that involved 3 to 15 visits have ranged from 0 to 20%. Participants who drop out will receive partial reimbursement for the time they donate. Eligible participants will be randomized to either CBT-I, or CCC+ in a 2:1 ratio. Randomization will be stratified by gender and smoking. Participants will be paid \$1060 for their complete participation.

During the study, study staff members will communicate with participants via phone, email, standard mail, or texts sent from a Duke-owned phone, based on participant preferences. Participants will be allowed to opt out of texting or emailing if they wish.

C.4. Interventions

C.4.1. Cognitive Behavior Therapy for Insomnia (CBT-I). The approach to CBT-I for the proposed study is based on CBT-I programs that have been practiced and studied by research team members (Karlin, Trockel, Tylor, Gimeno, & Manber, 2013; Manber, Carney, & Edinger, 2012). CBT-I is manualized in a session-by-session guide (Perlis, Jungquist, Smith, & Posner, 2005). [name] serves as a consultant and trainer on the nationwide dissemination of CBT-I. [name] will train study therapists to deliver CBT-I in accordance with the training approach adopted by the CBT-I dissemination effort (Karlin, Trockel, Tylor, Gimeno, & Manber, 2013). Further, [name] will be available for consultation regarding the training procedures and fidelity measures and methods.

C.4.2. Minimal Contact Control Condition. Participants assigned to the CCC will be contacted via WebEx or Zoom every week for eight weeks. To monitor their insomnia symptoms and mood, they will be asked to complete the PTSD Checklist and Insomnia Severity Index. Check-in calls will be audio-recorded. This will allow us to do fidelity ratings to ensure that participants are not receiving any sleep interventions, advice, etc. Please note that our lab has an SOP related to suicide risk assessment, and the study coordinator who makes the check-in calls has been trained in the use of the SOP. Participants

will be asked about any insomnia treatments they use/receive during usual care. At the end of the 6-month follow-up, participants randomized to this condition will be offered CBT-I.

C.4.3. Intervention Training and Fidelity. Study therapists will include [name] and two masters' level mental health providers. Each therapist will provide treatment in both arms. Masters' level therapists will be trained by [name]. Initial didactic training (covering session by session procedures, core components of CBT-I and SH+) will last three days and be followed by training cases. Therapists will be allowed to provide the intervention once they have demonstrated 100% competence and adherence with all required treatment elements. Therapists will meet weekly for supervision throughout the trial. All therapy sessions will be audio-recorded. A random selection of twenty percent will be rated for fidelity. In order to protect against drift, the frequency of fidelity checks will occur equally across the beginning, middle, and end of the intervention period. [name] will rate therapist treatment fidelity/adherence for recorded sessions using the adapted version of the *Yale Adherence and Competence Scale* (Carroll, 2000). In the CBT-I condition, recordings will be rated on the presence/absence of CBT-I elements. In the comparison condition, recordings will be rated on the presence of proscribed elements of CBT-I. In addition, recordings from both conditions will be rated on the presence/absence of nonspecific treatment elements (e.g., therapeutic alliance, patient expectancies). Feedback from fidelity checks will be provided to therapists. In addition, emergency procedures for suicidal and homicidal ideation have been well developed in our laboratory and these will be carefully followed for each participant. [name] will also provide consultation to [name].

C.5. Measures

We have experience assessing all the proposed measures and items discussed below. Table 1 summarizes the measures and the timepoints at which they are given.

Table 2. Study Measures					
Measure	Completer 1=[name] team, 2=[name] team	Time			
		Screen*	Baseline	PostTxt	6-Mon
Clinician Administered PTSD Scale	Trained interviewer ¹	X ²			
Structured Clinical Interview for DSM5	Trained interviewer ¹	X ²			
Duke Structured Interview for Sleep Disorders	Trained interviewer ²	X ¹			
Montreal Cognitive Assessment	Trained interviewer ¹	X ¹			
Traumatic Life Events Questionnaire	Participant	X ¹			
PTSD Checklist	Participant	X ¹	X	X	X
Beck Depression Inventory – II	Participant	X ¹	X	X	X
WHO Disability Assessment Schedule	Participant	X ¹			
WHO Quality of Life	Participant		X	X	X
Everyday Discrimination Scale	Participant	X ¹			
Short Form-36 Health Survey	Participant		X	X	X
Daily sleep diaries	Participant	X	X	X	X
Insomnia Severity Index	Participant	X ¹	X	X	X
Pittsburgh Sleep Quality Index with PTSD addendum	Participant		X	X	X

Epworth Sleepiness Scale	Participant	X ¹			
Medical Problems Checklist	Study coordinator ¹	X ¹			
STOP-BANG	Participant	X ¹			
Pre-Sleep Arousal Scale	Participant		X	X	X
Demographics measure	Participant	X ¹			
Fagerström Test for Nicotine Dependence	Participant	X ¹			
AUDIT-C	Participant	X ¹			
Leisure Time Exercise Questionnaire	Participant		X	X	X
Menopausal status	Participant		X		X
PEG	Participant	X ¹			
Medications List	Participant	X ¹	X	X	X
Insomnia Treatment Measure	Participant			X	Xau
Over-the-Counter Medications List	Participant	X ¹	X	X	X
Physiological Measures					
Actigraphy	Study staff ²		X	X	X
WatchPAT One sleep apnea assessment	Participant	X ²			
24-hour blood pressure assessment	Study staff ²		X	X	X
Flow mediated dilation	Study staff ²		X	X	X
24-hour urinary catecholamines	Participant ²		X	X	X
ASCVD risk	Study staff ²		X	X	X
Body Mass Index	Study staff ²		X	X	X

* Superscript 1 indicates that these procedures are completed at the first screen visit, and superscript 2 items are completed at the second screen visit.

C.5.1. PTSD, Depression, Alcohol Use Disorder and Quality of Life Measures. The Clinician-Administered PTSD Scale (CAPS; Weathers, Blake, et al., 2013) will be utilized to establish PTSD diagnosis. The CAPS is considered to be the gold standard for determining PTSD diagnosis. The Traumatic Life Events Questionnaire (TLEQ; Kubany, Hill, & Owens, 2003) is designed to assess exposure to traumatic events, and has an item to assess exposure to combat. Individual items/exposures can be summed to reflect a total exposure type score. PTSD symptom severity will be measured by the PTSD Checklist (PCL5) with criterion A (Weathers, Litz et al., 2013). Diagnoses other than PTSD will be assessed using the *Structured Clinical Interview for DSM-5* (SCID). The SCID has been shown to have good reliability (Williams, Gibbon, First, 1992) and includes modules that determine current and lifetime psychiatric disorders. PTSD symptom severity will be measured by the PTSD Checklist (PCL5 with criterion A; Weathers, Litz et al., 2013). The Everyday Discrimination Scale will measure the perceived frequency of chronic, routine and subtle experiences of unfair treatment that could be one dimension of perceived stress in our sample (Williams, Yu, Jackson, & Anderson, 1997). *Depressive symptoms* will be measured with the Beck Depression Inventory-II (Beck, Steer, & Brown, 1996). *Functional status* will be measured using the World Health Organization Disability Assessment Schedule 2.0 (WHO DAS-II), a 36-item self-report of functional disability designed to measure functioning and impairment over the past 30 days. The WHO DAS-II has exhibited excellent reliability and validity in prior research (Garin et al., 2010). *Quality of life* will be measured using the Short Form-36 Health Survey (SF-36; Ware & Sherbourne, 1992), which provides a physical health and mental health QoL summary score. The SF-36 has demonstrated reliability and validity in PTSD populations (Shiner, Watts, Pomerantz, Young-Xu, & Schnurr, 2011). We will also use the World Health Organization Quality of Life Scale, Brief Version (WHOQOL-BREF).

C.5.2. Insomnia and Sleep Measurement. Sleep measurement will include both subjective and objective measures. Subjective measures will include sleep diaries collected via interactive voice technology and self-report measures of sleep quality, insomnia severity, and perceived daytime sleepiness. Actigraphy will be employed as an objective measure of the sleep outcomes (TST, WASO, and SE).

C.5.2.1 Interview-Based Assessment. The *Duke Structured Interview for Sleep Disorders* (DSISD) is currently being revised to be consistent with DSM-V and the International Classification of Sleep Disorders, and will be administered to identify those meeting criteria for ID and rule out individuals having excluded co-morbid sleep disorders. The DSISD has been shown to have good reliability and validity (Edinger, Wyatt, & Olsen, 2009). The DSISD will be given during the first screening session.

C.5.2.2. Sleep Apnea Assessment. Following the DSISD and (completed at the enrollment visit), if a participant has scored a three or greater on the STOP BANG, the potential study participant will be sent home with a portable apnea screening device to wear for 1 complete night to rule out sleep apnea. The WatchPAT device (Itamar Medical) is a sensitive and specific assessment for identifying the presence of obstructive sleep apnea. The device requires that participants download an app that will sync with the device and transfer the data to WatchPAT's servers. Participants will be given the option of using their own personal phone or using a Duke-owned iPhone that they then return. In the event that the sleep evaluation reveals that a participant shows an apnea-hypopnea index (AHI) > 15 (i.e., more than 5 sleep apnea-hypopneas per hour of sleep) (Walczewska et al., 2011), participant will be notified that they are no longer eligible to continue, and will be encouraged to seek additional evaluation and treatment through their physician (Epstein et al., 2009).

In the event of any equipment malfunction, participants may be asked to repeat the WatchPAT home study. In order to reliably rule out obstructive sleep apnea, a minimum of 4 hours of recording time is required. Therefore, if participants notice any of the equipment coming off in the middle of the night, they will be instructed to reattach. If it is found that there is less than 4 hours of recording time, the participant will be asked to repeat the in-home study. To prevent this from occurring, participants will be given detailed instructions and staff will provide an in-person demonstration to show them how to properly use the device.

C.5.2.3. Actigraphy. Actiwatch Spectrum Plus® (Respironics, Inc.) are wristwatch style actigraphs containing a calibrated accelerometer that samples, digitizes, and stores movement activity. When interfaced with a computer, a scoring algorithm provides estimates of various sleep parameters. When costly PSG is not feasible and sleep staging outcomes are not the focus of research, wrist actigraphy is recommended as an essential measure of rest-activity patterns in insomnia research (Buysse, Ancoli-Israel, Edinger, Lichstein, & Morin, 2006). The following sleep metrics will be collected over a one week period at baseline, post-treatment, and 6-month follow-up: Time in Bed (TIB), TST, WASO, and sleep fragmentation (Ancoli-Israel, Cole, Alessi, Chambers, Moorcroft, & Pollack, 2003; Blackwell et al., 2008; Littner et al., 2003; Marino et al., 2013; Morgenthaler et al., 2007; Sadeh & Acebo, 2002; Sadeh, Hauri, Kripke, & Lavie, 1995; Thorpy et al., 1995). These parameters will also be collected during the entire 8-

week treatment period.

Sleep duration will be defined as TST (calculated by subtracting all periods of wakefulness from the time spent in bed). WASO is calculated by summing wakefulness periods after initial sleep onset and before final awakening. Sleep efficiency is defined as the ratio of total sleep time divided by TIB (TST/TIB). Sleep fragmentation (a secondary outcome) is defined as the sum of percent mobile and percent immobile bouts less than 1-minute duration to the number of immobile bouts for a given interval (Respironics Incorporated, 2008). Actigraphy will be used as the primary source for these variables (Lauderdale, Knutson, Yan, Liu, & Rathouz, 2008). Scoring of actigraphy data will proceed in accordance with the guidelines by the Society of Behavioral Sleep Medicine (Ancoli-Israel et al., 2015). The sleep diary will include queries about removal of the actigraphy watch from the wrist, and unusual activities during the monitoring period (e.g., travel), and these factors will be considered when scoring. The event marker will be used as the primary method for establishing “into bed” and “out of bed” times. However, when study participants fail to press the event marker, (i.e., no marker on actigraphy output), light sensor data and sleep diaries will be combined with accelerometry data to establish “into and out of bed” times.

C.5.2.4. Daily Sleep Diaries. Subjective sleep estimates will be obtained concurrent with actigraphy, using a Qualtrics survey. Participants will record their sleep using the recently developed consensus sleep diary (Carney et al., 2012) to assure comparability across insomnia research studies. Sleep diaries will be used to calculate averages for: TIB, sleep onset latency (SOL) (Marino et al., 2013), TST, WASO, and SE. The sleep diary is considered the gold standard of self-reported sleep (Buysse et al., 2006). We will use Duke Qualtrics to gather the daily sleep diaries.

